**Table 9-1 Classification and Rationale for Correlation Determination Results of AEs in Drug Clinical Studies**

5-category method	Rationale for determination	2-category method
Definitely related	
 
• Whether there is reasonable temporal relationship
 
• Whether it conforms to the known mechanism of action, properties of the drug or known adverse reactions
 
• Positive de-challenge test
 
• Positive re-challenge test
 
	Related

5-category method	Rationale for determination	2-category method
Probably related	
 
• Whether it is not justified by other reasons
 
	
Possibly related	
 
• Whether there is reasonable temporal relationship
 
• Whether it conforms to the known mechanism of action, properties of the drug or known adverse reactions
 
• Positive de-challenge test
 
• Lack of evidence for a positive re-challenge
 
• Whether it is not justified by other reasons
 
	
	
 
• There is a reasonable temporal relationship;
 
• Lack of evidence for a positive re-challenge;
 
• It is manifested as any of the following conditions: 
 
a) The AE is consistent with the known mechanism of action, characteristics or known adverse reactions of the drug, de-challenge test is positive, but the AE can also be reasonably explained by other factors;
 
b) The AE is consistent with the known mechanism of action, characteristics or known adverse reactions of the drug, there is a lack of evidence for a positive de-challenge, and the AE cannot be reasonably explained by other factors;
 
c) The AE is not consistent with the known mechanism of action, characteristics or known adverse reactions of the drug, de-challenge test is positive, and the AE cannot be reasonably explained by other factors;
 
d) The AE is not consistent with the known mechanism of action, characteristics or known adverse reactions, there is a lack of evidence for a
 
 
 
	

5-category method	Rationale for determination	2-category method
	positive de-challenge, and the AE cannot also be reasonably explained by other factors;	
Unlikely related	
 
• Temporal relationship cannot be ruled out
 
• Lack of evidence for a positive de-challenge
 
• Lack of evidence for a positive re-challenge
 
• It is manifested as any of the following conditions: 
 
a) Although the AE is consistent with the known mechanism of action, characteristics or known adverse reactions, it can be more reasonably explained by other factors;
 
b) The AE is not consistent with the known mechanism of action, characteristics or known adverse reactions, and can be reasonably explained by other factors;
 
 
 
	Unrelated
Not related	
 
• There is no reasonable temporal relationship
 
• It does not conform to the known mechanism of action, properties of the drug or known adverse reactions
 
• Lack of evidence for a positive de-challenge
 
• Lack of evidence for a positive re-challenge
 
• It can be justified by other reasonable reasons
 
	

### 9.3 Determination of the Severity

The severity of AEs will be recorded according to the National Cancer Institute (NCI) Common Terminology Criteria for Adverse Events (CTCAE) Version 5.0. For AEs not listed in NCI-CTCAE, its severity can be graded as follows:

- **Grade 1:** Mild; asymptomatic or mild symptoms; clinical or diagnostic observations only; or intervention not indicated.
- **Grade 2:** Moderate; minimal, local or noninvasive intervention indicated; limiting

age-appropriate instrumental activities of daily living (instrumental activities of daily living refer to preparing meals, shopping for groceries or clothes, using the telephone, managing money, etc.);

- **Grade 3:** Severe or medically significant but not immediately life-threatening; hospitalization or prolongation of hospitalization indicated; disabling; limiting self-care ADL (self-care ADL refer to bathing, dressing and undressing, feeding self, using the toilet, taking medications, and not bedridden);
- **Grade 4:** Life-threatening, urgent intervention indicated;
- **Grade 5:** Adverse event-related death.

## **9.4 Collection, Recording and Reporting of AEs**

### **9.4.1 Collection and Recording of AEs and SAEs**

#### **9.4.1.1 Collection Time of AEs**

AEs are collected in this trial from the time the subject receives the investigational product (i.e., TJ0113 capsules or placebo) until the end of the follow-up period. Supplementary description is as follows:

- Untoward medical occurrences (including abnormalities at baseline) that newly occur or worsen relative to pre-signing state from subject's signing ICF to the first dose of the investigational product, if assessed by the investigator as related to the subject's participation in this trial (such as a protocol-specified procedure or invasive test), should be recorded and reported as AEs, otherwise should be recorded as medical history;
- The investigator needs to collect all AEs (regardless of whether it is causally related to the investigational product or related to clinical procedure) from the first dose of the investigational product to the end of the follow-up period;
- AEs that occur after the follow-up period must also be collected and recorded if the investigator considers that it is related to the investigational product (including SAEs) after awareness.

#### **9.4.1.2 Recording of AEs**

The investigator or other designee will be responsible for monitoring, recording and reporting events that meet the definition of AEs/SAEs.

At each visit during the entire study period, the investigator or his/her designee should ask the

subject non-directive questions to learn about the occurrence of AEs/SAEs, and may also find AEs/SAEs through the subject's spontaneous reports, physical examinations, laboratory tests or other assessments during the visit or non-visit period. The subject or his/her caregiver may also report AEs occurring during the trial.

For any unexplainable or unexpected laboratory abnormalities of clinical significance throughout the study period, retest should be performed as soon as possible and the abnormality should be followed up until returning to the normal range and/or adequate explanation can be given for the abnormality. The investigator should clearly mark the laboratory results out of normal range and indicate whether they are of clinical significance or not.

All AEs must be followed up until they have clinically recovered, stabilized, return to the screening or baseline level (if baseline level is known), the subject is lost to follow-up (e.g., no more information is available or the subject/caregiver refuses to provide any information), or dead. This means that further follow-up observations may be required even after the last protocol-specified visit, and the monitoring team may require the investigator to perform additional follow-up.

All AEs occurring within the collection time limit specified in this protocol must be completely recorded (after the end of the trial, the collection of follow-up data for subjects with ongoing AEs does not affect the on-time database lock after the end of the trial).

For the recording of AEs/SAEs, a single diagnosis or syndrome should be used to describe their term as far as possible. The documentation should be supported by original documents and each event should be described in detail, including:

- Term of AEs (use the term for a sign, symptom, diagnosis, or syndrome);
- Onset date, ongoing or not, end date;
- Severity;
- Investigator's judgment of the causality between the event and investigational product or study procedure, including details of the suspected procedure;
- The actions taken with investigational product may include dose not changed, temporarily discontinued, dose reduced, drug withdrawn, not applicable, and

unknown;

- Event outcomes: ① recovered/resolved; ② recovering/resolving; ③ not recovered/not resolved/ongoing; ④ recovered/resolved with sequelae; ⑤ fatal; and ⑥ unknown;
- Seriousness: Whether it is an SAE or not;
- Drug therapies and other interventions given to correct the AE.
  - None;
  - Drug therapy;
  - Non-drug intervention;
  - Drug therapies and non-drug interventions.

In addition, the investigator should collect other information required by the sponsor.

#### **9.4.1.3 Precautions for Recording of AEs/SAEs**

##### **Diagnosis versus signs and symptoms**

The diagnosis that is available should be recorded rather than single symptom or sign. However, if the symptoms and signs cannot be categorized as a single diagnosis during reporting period, each single event should be recorded as AE or SAE. If the diagnosis is confirmed later, the AE previously reported based on signs and symptoms should be canceled and be replaced with an AE report based on a single diagnosis, noting that the start date should be the start date of the first symptom used for the final diagnosis.

##### **AEs secondary to other events**

In general, for events secondary to other AEs (such as cascading events or clinical sequelae), they should not be recorded as separate AEs, except for severe or serious secondary events. If the secondary event is medically significant and the two events occurred independently of each other, the secondary event should be recorded as a separate AE in the eCRF. For example:

- If vomiting has caused severe dehydration, two AEs should be separately reported on the eCRF.
- If severe gastrointestinal bleeding has caused renal failure, two AEs should be separately reported on the eCRF.
- If dizziness caused a fall followed by a fracture, three AEs should be separately

reported on the eCRF.

- If neutropenia caused infection, two AEs should be separately reported on the eCRF.
- If it is not clear whether the events are interrelated, all AEs should be recorded separately in the AE Record of the eCRF.

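### Protocol 9.4.1.3 gives incompatible instructions on adverse events caused by another adverse event, so sites may record the same non-severe event differently

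*Protocol*

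**What the plan says.** Protocol 9.4.1.3, under AEs secondary to other events, contains four kinds of instruction.

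- **General rule.** Of events secondary to another AE, it says that in general "they should not be recorded as separate AEs, except for severe or serious secondary events".
- **Further exception.** A separate record is also required under this condition: "If the secondary event is medically significant and the two events occurred independently of each other".
- **Examples.** These follow directly from that exception. One has a secondary event that is itself severe: "If vomiting has caused severe dehydration, two AEs should be separately reported on the eCRF". Another covers a chain of three events and sets no severity condition on any of them: "If dizziness caused a fall followed by a fracture, three AEs should be separately" entered in the eCRF. A third does the same for a secondary infection: "If neutropenia caused infection, two AEs should be separately reported on the eCRF". The remaining one is renal failure caused by severe gastrointestinal bleeding, counted as two AEs.
- **Default.** "If it is not clear whether the events are interrelated, all AEs should be recorded separately in the AE Record of the eCRF".

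Two neighbouring sections set the general duty. Protocol 9.4.1.1, for the time between first dose and the close of follow-up, states: "The investigator needs to collect all AEs (regardless of whether it is causally related to the investigational product", and likewise for links with trial procedures. Protocol 9.4.1.2 states: "All AEs occurring within the collection time limit specified in this protocol must be completely recorded".

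SAP 6.12.2 summarises TEAEs by SOC and PT, and all TEAEs and SAEs also by highest CTCAE grade. Percentages count subjects, not occurrences. No step recovers an event that was never entered.

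**The concern.** A secondary event is by definition one that another event led to. The further exception asks that it also be independent of that event, so read literally the exception is empty. What is left is the general rule, under which a secondary event earns its own row only if it is severe or serious. Protocol 9.3 makes severe equivalent to Grade 3, so the events left out are non-serious events of Grade 1 or 2. Grade 2 includes events that limit instrumental daily activities, so these are not only trivial events.

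The examples point the other way, and a site cannot follow both. Safety is a secondary objective and the PT tables are the main place where a reader looks for particular harms. If recording depends on which sentence a site relied on, PT counts mix two conventions. The loss also scales with the number of initiating events, which is a post-randomisation outcome, so it need not be equal across arms even though the rule is the same for all.

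**Working it through.** The documents give no figure to reproduce: the trial has no formal sample-size assumptions and states no expected AE rates. The check is therefore mainly a comparison of text.

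| Event | General rule with its exception | Examples and default |
|---|---|---|
| Non-severe, non-serious infection caused by neutropenia | No separate AE | Separate AE |
| Non-severe, non-serious fall caused by dizziness, fracture following | No separate AE for the fall | Separate AE for each of the three |
| Same fall, no fracture | No separate AE | Not literally covered; by analogy, separate |
| Severe dehydration caused by vomiting | Separate AE | Separate AE |
| Renal failure caused by severe bleeding | Separate AE if severe or serious, as it normally would be | Separate AE |
| Link between events unclear | Rule not triggered | All recorded separately |

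The conflict is confined to the first three rows: events that are clearly linked, non-severe and non-serious.

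**Illustration, on assumed rates only.** Let *n* = 50 per arm (the planned size). The other inputs are assumptions:

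- *b*: background incidence of the secondary term, 2%.
- *p*: incidence of the initiating AE, 10% on placebo and 10%, 20% or 30% on drug.
- *q*: probability that an initiating AE leads to a clearly linked, non-severe, non-serious secondary event, 25% to 75%.

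Incidence if every such event is recorded: 1 − (1 − *b*)(1 − *pq*). Events left out per arm under the literal rule: *npq*. Difference between arms if all are recorded: (1 − *b*)(*p*drug − *p*placebo)*q*.

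- Drug 30%, placebo 10%, *q* = 50%: 1 − 0.98 × 0.85 = 16.7% against 1 − 0.98 × 0.95 = 6.9%, a difference of 9.8 points, or about 5 subjects in 50. Left out: 50 × 0.30 × 0.50 = 7.5 events on drug and 50 × 0.10 × 0.50 = 2.5 on placebo.
- Drug 30%, *q* from 25% to 75%: difference 0.98 × 0.20 × *q* = 4.9 to 14.7 points.
- Drug 20%, *q* from 25% to 75%: 0.98 × 0.10 × *q* = 2.45 to 7.35 points.
- Drug 10%, same as placebo: difference 0, with equal loss in both arms (2.5 and 2.5 events at *q* = 50%).

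Under full literal compliance the recorded incidence is *b* in both arms, so the recorded difference is 0 by construction. If only a share *c* of these events is handled under the rule and the rest under the examples, the recorded difference is (1 − *b*)(*p*drug − *p*placebo)*q*(1 − *c*). In the first case above, an assumed *c* of one half gives 0.98 × 0.20 × 0.50 × 0.50 = 4.9 points, between 9.8 (*c* = 0) and 0 (*c* = 1).

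The initiating AE keeps its own row throughout (30% against 10% in that case), and the number of subjects with any TEAE does not change.

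**The case against.** The strongest reply is that this is a recording convention with awkward wording. Not splitting trivial cascade events is defensible, and Protocol 9.4.1.2 itself prefers a single diagnosis or syndrome. The rule is qualified as general practice and concerns separate rows. Severe and serious secondary events are kept, and so is everything whose link is uncertain. The fall-with-fracture and infection cases are ones that the examples expressly tell sites to record. Sections 9.4.1.1 and 9.4.1.2 chiefly set the collection window and completeness, so the clash with them is looser than the clash with the examples. Laboratory, vital-sign, physical-examination and ECG results are summarised separately in SAP 6.12.3 to 6.12.6.

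Most of this stands, and it limits the size of the problem. It does not remove the inconsistency. The general qualifier gives sites no criterion for departing from the rule. The default helps only where the link is in doubt. The separate summaries would not generally capture a fall or a clinical infection as an event. That the examples require recording is precisely what makes the instruction contradictory.

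On differential loss, the reply is also largely right. Investigators are blinded, so one instruction applies to all arms. Protocol 2.4.2 lists decreased neutrophil count among the commonest phase I TEAEs (8.3% in each of the single- and multiple-dose parts), but reports similar incidences by PT on drug and placebo. Dizziness is not among the phase I events named there. Protocol 11.4.4.2 and SAP 6.12.2 plan descriptive AE summaries, with no between-arm test.

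**Conclusion.** The point holds as an inconsistency that should be corrected. The general rule and the independence condition cannot be reconciled with the fall, fracture and infection examples, and they sit poorly with the all-AE duties in 9.4.1.1 and 9.4.1.2. The likely result is uneven recording between sites and a possible undercount of clearly linked, non-severe, non-serious events in the SOC/PT tables. Because severe secondary events are kept, the grade table could also be tilted.

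A reader might infer more: that harms the drug causes through another event disappear from its arm, or that a difference in such a term would always be recorded as nil. The documents do not support either. The initiating event remains visible, and they do not show that the drug raises initiating events. The nil result follows only from assuming that every site applies the first sentence literally and ignores the examples. The figures above are conditional on assumed rates and on that compliance; they show direction and mechanism, not an expected bias.

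**What to change.** In the AEs secondary to other events paragraph of Protocol 9.4.1.3, delete the independence condition, which is the second half of "If the secondary event is medically significant and the two events occurred independently of each other". State that a medically significant, clinically distinct secondary event, such as the fall, fracture or infection in the examples, is recorded as its own AE whether or not it is severe or serious. Keep the examples and the default for unclear links. Minor cascade events that are not medically significant can stay unsplit, so the convention survives where it is reasonable. Carry the same wording into the eCRF completion instructions, so that sites work from one text.

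The cost is one paragraph of protocol text and a few more AE rows, with somewhat higher occurrence counts. Any-TEAE subject incidence does not change, because the initiating event is already counted, and no SAP method needs altering.

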### **Persistent or recurrent AEs**

Persistent AEs are AEs that persist without any remission between the two evaluation time points of the subject. If the event meets the seriousness criteria, it is an SAE. The investigator should report it to the sponsor and the Contract Research Organization (CRO) designated by the sponsor within 24 hours of awareness. In such case, the AE should be updated to change the AE from "non-serious" to "serious", the date when the AE developed into SAE should be recorded, and all the information fields related to SAE should be filled in.

Recurrent AEs refer to AEs that have resolved or resolved with sequelae, but then reoccur. AEs that reoccur should be recorded separately.

### **Abnormal laboratory values and vital signs**

Not all abnormal laboratory values or vital signs are reportable as AEs. An AE must be reported if the laboratory test or vital sign meets any of the following criteria:

- Accompanied by clinical symptoms;
- Resulting in changes in the study treatment (e.g. dose adjustment, treatment interruption or discontinuation);
- Requiring medical intervention (e.g., potassium supplementation to treat hypokalemia) or resulting in changes in concomitant therapies;
- Clinically significant results at the investigator's discretion.

The investigators are responsible for reviewing all the abnormal laboratory findings and vital signs, and determine whether to record them as AEs.

If clinically significant abnormal laboratory tests or abnormal vital signs are manifestations of certain disease or syndrome (e.g., alkaline phosphatase and bilirubin increase more than 5 times the upper limit of normal, which are caused by cholecystitis), only the diagnosis is recorded (i.e., cholecystitis). Conversely, abnormal laboratory tests or abnormal vital signs should be recorded. Moreover, it should be indicated whether the test value is higher or lower

than the normal range (for example, it should be recorded as "blood potassium increased" instead of "abnormal blood potassium"). If there is a standard clinical term corresponding to abnormal laboratory tests or abnormal vital signs, the clinical term should be recorded. For instance, serum potassium increasing to 7.0 mEq/L should be recorded as "hyperkalemia".

#### **9.4.2 Reporting of SAEs**

For all SAEs that occur within the collection time limit specified in this protocol, the investigator must fill in, sign and date the SAE Report Form within 24 hours of awareness, immediately report it to the sponsor (or the CRO appointed by the sponsor).

In case of reports involving death events, the investigator should provide the sponsor and Ethics Committee with other necessary information, such as autopsy report and final medical report.

The investigator should provide detailed written follow-up reports in a timely manner. For follow-up information of SAEs, the reporting method and time limit are the same as those for the initial report.

Time for collecting SAEs:

- Only SAEs related to protocol-specified procedure or invasive test, etc. will be reported from subject's signing ICF to the first dose of the investigational product.
- The investigator needs to collect and report all SAEs (regardless of whether it is causally related to the investigational product or related to clinical procedure) from the first dose of the investigational product to the end of the follow-up period;
- SAEs that occur after the end of the clinical trial or the end of the follow-up until the conclusion of the review and approval is obtained, if assessed by the investigator that the relevance to the investigational product cannot be ruled out, should be informed to the sponsor (or the CRO appointed by the sponsor) within 24 hours of awareness.

#### **9.4.3 Reporting of SUSARs**

The sponsor (CRO appointed by the sponsor) should comprehensively analyze, evaluate and judge the safety information received of any sources in a timely manner, including severity, correlation with the investigational product and whether it is an expected event, as well as

report in an expedited manner depending on the nature (category) of the event within the time limit set out by the regulatory authorities. The sponsor (CRO appointed by the sponsor) should expeditedly report SUSARs to all investigators and clinical trial institutions participating in the study, Ethics Committee, drug regulatory authorities and health authorities within specified time limit.

The processing and expedited reporting of SUSAR reports will be completed in accordance with Good Vigilance Practice and FAQs for Expedited Reporting of Safety Data during Drug Clinical Trials (V2.0).

SUSARs occurring after the end of the clinical trial and before obtaining the approval conclusion will be reported in the same manner as for expedited reporting before the end of trial.

For the SUSAR report and clinical trial-related safety information provided by the sponsor, the investigator should sign and read it in time, and report to the clinical trial institution and the Ethics Committee.

